3 EXPERIMENTAL PLAN

3.1 STUDY DESIGN

This is a Phase 1b safety and tolerability single-sequence study in which subjects on a stable regimen of Tyvaso will switch to a corresponding dose of TreT. At Baseline, subjects currently taking stable doses of Tyvaso (6 to 12 breaths QID) will take a dose of Tyvaso in the clinic and undergo PK assessments, safety assessments, and a 6MWT. Following the in-clinic assessments, subjects will switch from Tyvaso to the corresponding dose of TreT and take their first dose of TreT in the clinic. Following 3 weeks of treatment with TreT, subjects will return to the clinic and receive 1 dose of TreT and undergo PK assessments, safety assessments, and a 6MWT as performed at the Baseline Visit.

Following the Week 3 Visit, subjects will be offered the opportunity to participate in the Optional Extension Phase of the study. Subjects who elect to discontinue TreT at the end of the Treatment Phase will return to the clinic in 2 weeks for an End of Study Visit. Subjects who elect to enter the Optional Extension Phase will remain on TreT and attend study visits every 8 weeks until the study is terminated or the drug/device becomes commercially available. If the subject discontinues TreT prematurely during the Optional Extension Phase, he/she must return to the clinic as soon as possible for an Early Termination Visit.

[figure not shown]
Screening Phase: Prospective subjects will be assessed during the Screening Phase to determine eligibility for the study. The Screening Visit must occur within 14 days prior to Baseline. During this Screening Phase, eligible subjects will sign the Informed Consent Form (ICF) and undergo screening assessments. Subjects who satisfy all eligibility criteria during the Screening Phase may return to the clinic at Baseline for enrollment. If subjects are able to satisfy all eligibility criteria on the same day, a combined Screening/Baseline Visit may be conducted.

Treatment Phase: The Treatment Phase consists of 2 study visits to the clinic separated by 3 weeks of treatment with TreT. At Baseline, subjects will receive 1 dose of Tyvaso in the clinic and undergo PK assessments (at the following timepoints: 15 minutes before dose and 5, 10, 15, 30, 45, 90, 120, 180, 240, and 300 minutes after dose), safety assessments, and a 6-Minute Walk Test (6MWT). No additional dose of Tyvaso will be administered, nor will TreT be started, until after the PK sampling assessment is complete. Following these assessments, subjects will be assigned a corresponding dose of TreT based upon their current stable Tyvaso dose and will receive the first dose of TreT in the clinic. Each subject will receive TreT QID by oral inhalation for 3 weeks. Following 3 weeks of treatment, subjects will return to the clinic and receive 1 dose of TreT in the clinic and undergo PK assessments, safety assessments, and a 6MWT as performed at the Baseline Visit. Questionnaires evaluating patient preference for inhaled treprostinil devices and patient-reported PAH symptoms and impact will also be administered. At each study visit, AEs will be assessed, vital signs will be recorded, and a physical examination (PE), including oropharyngeal examination, will be performed. Following the Week 3 Visit, subjects may choose to participate in the Optional Extension Phase of the study. If the subject does not elect to participate in the Optional Extension Phase of the study, he/she must

discontinue TreT, may resume Tyvaso therapy, and must return to the clinic 2 weeks after TreT discontinuation for an End of Study Visit. Blood samples for an optional evaluation of change in biomarkers (specific targets to be determined) will be collected at the Baseline Visit and Week 3 Visit. An additional blood sample for an optional evaluation of whole genome sequence will be collected at the Baseline Visit.

Optional Extension Phase: The Optional Extension Phase will occur following completion of the Treatment Phase and continue with clinic visits every 8 weeks until the study is terminated for any reason or the drug/device becomes commercially available. To be eligible for the Optional Extension Phase, subjects must complete the Treatment Phase, elect to continue TreT, and agree to attend follow-up visits in the clinic. Dosing titration will be encouraged during the Optional Extension Phase; the dose of TreT should be titrated upward, as clinically tolerated, to identify a maximum stable dose in each subject. Subjects who discontinue TreT must complete an Early Termination Visit as soon as possible. A blood sample for an optional evaluation of change in biomarkers will be collected at the Week 51 Visit.

Figure 3-1 Study Flow Chart

3.2 OVERALL SCHEDULE OF TIMES AND EVENTS

Table 3-1 Overall Schedule of Times and Events

Study Phase		Combined Screening &	Treatment Phase		End of Study/Early Termination	Optional Extension Phase ^d Week 11 then
Study Visit	Screening ^a	Baseline ^{a,b}	Baseline ^b	Week 3 ^c	Visit ^{c,k}	every 8 weeks ^d
Study Day	-14 to -1	1	1	21		
Informed Consent	X	X				
Inclusion/Exclusion Criteria	X	X	X			
PQ-ITD ^m		X	X	X	X	
PAH-SYMPACT ^m		X	X	X	X	X
Inspiratory Criteria Assessment	X	X	X			
Demographics	X	X				
Medical History	X	X				
Physical Examination	X	X	X	X	X	X
Vital Signs ^e	X	X	X	X	X	X
Urine Pregnancy Testh	X	X	X	X	X	X
Clinical Laboratory Assessments		X	X	X	X	X
12-lead ECG ⁿ		X	X		X	
PK Blood Samples ^j		X	X	X		
Blood Sample for Biomarker Evaluation (Optional) ^f		X	X	X		X
Blood Sample for Whole Genome Sequencing (Optional) ^g		X	X			
6MWT ^b	X	X	X	X	X	X
Dosing Instructions/Dosing Diary/TreT Accountability		X	X	X	X°	X

Study Phase		Combined	Treatm	ent Phase	End of Study/Early	Optional Extension Phase ^d
Study Visit	Screening ^a	Screening & Baseline ^{a,b}	Baseline ^b	Week 3 ^c	Termination Visit ^{c,k}	Week 11 then every 8 weeks ^d
Telephone/Email Contact ¹		X	X	X		X
AEs/SAEs ⁱ	X	X	X	X	X	X
Concomitant Medications	X	X	X	X	X	X

Abbreviations: 6MWT, 6-Minute Walk Test; ECG, electrocardiogram; AE, adverse event; PK, pharmacokinetic; PAH-SYMPACT, Pulmonary Arterial Hypertension Symptoms and Impact; PQ-ITD, Preference Questionnaire for Inhaled Treprostinil Devices; SAE, serious adverse event; TreT, Treprostinil Inhalation Powder

- a Screening Visit assessments can occur up to 14 days prior to the Baseline Visit. If subjects are able to satisfy all eligibility criteria on the same day, Screening assessments can be combined with baseline assessments.
- b If the subject has not previously undergone a 6MWT at the study site on the course intended for use during the study, a practice test must be conducted at the Screening Visit and must precede the baseline 6MWT by at least 1 day. To assist with subject scheduling, the baseline 6MWT may be conducted within 24 hours prior to PK sampling (eg, previous day). If the baseline 6MWT is conducted the day prior to PK sampling, then the Week 3 6MWT must also be conducted on the day prior to PK sampling for consistency. If the 6MWT is conducted concurrently with the PK sampling, it should occur between 45 to 60 minutes after the most recent dose. If the Baseline 6MWT is conducted concurrently with PK sampling, then the Week 3 6MWT must also be conducted concurrently with PK sampling. All 6MWTs should be conducted between 10 to 60 minutes after the most recent dose. Prior to the start of each 6MWT, the subject should rest (seated) for at least 10 minutes.
- c The visit window for the Week 3 Visit and the End of Study Visit is ±3 days.
- d The visit window for the Optional Extension Phase Visits is ±5 days. If the subject consents to the Optional Extension Phase of the study, the study will continue with clinic visits every 8 weeks until the study is terminated for any reason or the drug/device becomes commercially available. Additional unscheduled visits may be scheduled as required, for example, to address AEs or to titrate doses as appropriate.
- e Vital signs must be collected after 5 minutes of rest (seated); no other measurements or procedures should be performed during this 5-minute period. When possible, vital signs should be collected prior to the 6MWT. If vital signs cannot be obtained prior to the 6MWT, then they should be obtained after recovery from the 6MWT.
- f For subjects consenting to the optional biomarker sample. For subjects continuing in the Optional Extension Phase, this sample is only required at Week 51 (or upon early termination if prior to Week 51).
- g For subjects consenting to the optional whole genome sequencing sample.
- h For women of childbearing potential.
- i All AEs will be documented from the time of informed consent until the time screen failure is documented, or until the subject is either discontinued from the study or all End of Study Visit assessments have been completed and should be followed until either resolution (or return to normal or baseline values), until they are judged by the Investigator to no longer be clinically significant, or for at least 30 days if the AE extends beyond the final study visit.
- The in-clinic dose of Tyvaso or TreT will be inhaled in the clinic, followed by serial PK assessments (see Section 3.3.1.1 for details).
- k If a subject elects to discontinue TreT at the end of the Treatment Phase, an End of Study Visit must be completed within 2 weeks (±3 days). If a subject is discontinued from the study prematurely, an Early Termination Visit should be completed as soon as possible. Subjects who permanently discontinue TreT are encouraged to undergo premature termination assessments prior to discontinuing TreT or as close as possible to the last dose of TreT.

- 1 At least weekly telephone contact is required during the 3-week Treatment Phase. During the optional extension phase, telephone contact must occur at least every 2 weeks between Week 3 and Week 11, and must occur at least monthly after Week 11 to encourage uptitration in addition to assessing AEs and concomitant medications. Contact may be replaced by a face-to-face interaction on the weeks where study visits occur and the information can be obtained during the visit. Subjects may be contacted via email in lieu of a telephone call. A copy of the emails and/or telephone contact sheets must be documented in the subject's source documentation. Email should not replace direct follow-up by phone or in the clinic for clinically significant AEs or other emergent issues.
- m The PQ-ITD and PAH-SYMPACT should be completed as the first assessments during the visit before the subject completes any of the other scheduled visit assessments (after informed consent is obtained). The PQ-ITD for TreT will only be administered during an Early Termination Visit if the subject discontinues during the 3-week Treatment Phase. The PAH-SYMPACT will be conducted at Week 11 visit only in the Optional Extension Phase.
- n The 12-lead ECG should be recorded after at least 5 minutes of rest.
- o Only drug accountability and dosing diary will be performed at the End of Study Visit or Early Termination Visit.

Table 3-2 Schedule of Events for Dosing and Pharmacokinetic Sampling - Baseline and Week 3 Visit

Time Relative to Dose (minutes)	Activitya	
-15±3 (predose)	PK Sample 1	
0 (dose)	Administer dose	
5±3	PK Sample 2	
10±3	PK Sample 3	
15±3	PK Sample 4	
30±3	PK Sample 5	
45±3	PK Sample 6	
90±3	PK Sample 7	
120±3	PK Sample 8	
180±3	PK Sample 9	
240±3	PK Sample 10	
300±3	PK Sample 11	

Abbreviations: 6MWT, 6-Minute Walk Test; PK, pharmacokinetic

a If the baseline 6MWT is conducted concurrently with the PK sampling, then the Week 3 6MWT must also be conducted concurrently with PK sampling. If the 6MWT is conducted concurrently with the PK sampling, it should occur between 45 to 60 minutes after the most recent dose.

3.3 CLINICAL ASSESSMENTS

3.3.1 Efficacy Assessments

3.3.1.1 Pharmacokinetic Assessments

Fifteen minutes prior to administration of the in-clinic dose of Tyvaso or TreT at the Baseline Visit and the Week 3 Visit, qualified study personnel, as delegated by the Investigator, will obtain a predose blood sample of approximately 5 mL via an indwelling IV catheter or by direct venipuncture. The predose sample should occur at least 4 hours after the subject's last dose of Tyvaso or TreT. Subsequent serial blood samples of approximately 5 mL will be taken in a similar manner at the following timepoints (±3 minutes): 5, 10, 15, 30, 45, 90, 120, 180, 240, and 300 minutes after Tyvaso or TreT administration (see Table 3-2). Blood samples will be analyzed for treprostinil plasma concentrations.

3.3.1.2 6-Minute Walk Test

The 6MWT is a validated and reliable measure of exercise capacity in patients with chronic respiratory diseases (Holland 2014). This study will utilize an unencouraged 6MWT to minimize potential bias associated with encouragement. All 6MWTs will be conducted by qualified, trained personnel in a designated 6MWT area which meets the requirements as described in Appendix 15.1. Subjects who have not previously performed the 6MWT at the study site on the course intended for use during the study must perform a practice 6MWT at the study site at least 1 day prior to the Baseline Visit. Subjects will perform a peak 6MWT at Baseline to confirm their eligibility to participate in the study (6MWD ≥150 m per Inclusion Criterion 7). Prior to the start of each 6MWT, the subject must rest (seated) for at least 10 minutes. To assist with subject scheduling, the baseline 6MWT may be conducted within 24 hours prior to PK sampling (eg. previous day). If the baseline 6MWT is conducted the day prior to PK sampling, then the Week 3 6MWT must also be conducted on the day prior to PK sampling for consistency. Peak 6MWTs will be conducted at study visits as specified in Table 3-1. All 6MWTs should be conducted between 10 to 60 minutes after the most recent dose of Tyvaso or TreT. If the 6MWT is conducted concurrently with the PK sampling, the 6MWT should occur between 45 to 60 minutes after the most recent dose. Subjects receiving supplemental oxygen during the Baseline 6MWT should continue to receive the same flow rate at the Week 3 6MWT. Pulmonary rehabilitation

may not be introduced to a subject's treatment regimen within 12 weeks prior to Baseline through the Week 3 Visit.

3.3.1.3 Preference Questionnaire for Inhaled Treprostinil Devices

The Preference Questionnaire for Inhaled Treprostinil Devices (PQ-ITD) will be administered at the Baseline Visit to assess the subject's current use of the Tyvaso Inhalation System and at the Week 3 Visit or the Early Termination Visit to assess the subject's use of the TreT Inhaler. The PQ-ITD for TreT will only be administered during an Early Termination Visit if the subject discontinues during the 3-week Treatment Phase. The PQ-ITD should be completed as the first assessment during the visit before the subject completes any of the other scheduled visit assessments. Copies of the PQ-ITD (Tyvaso and TreT versions) can be found in the Study Reference Manual and will only be administered at study sites where available.

3.3.1.4 PAH-SYMPACT Questionnaire

The PAH-SYMPACT is a patient reported outcome (PRO) questionnaire consisting of 11 symptom and 11 impact items, which was developed based on interviews of PAH patients and following PRO guidance from the US Food and Drug Administration (FDA) (McCollister 2016, Chin 2018).

The PAH-SYMPACT questionnaire will be administered at the Baseline Visit, Week 3 Visit, and the Week 11 Visit (subjects participating in the Optional Extension Phase) or the Early Termination Visit. Detailed instructions on how to administer the PAH-SYMPACT to subjects will be provided to the sites. A copy of the PAH-SYMPACT questionnaire can be found in the Study Reference Manual and will only be administered at study sites where available.

3.3.1.5 Optional Biomarker and Optional Whole Genome Sequencing

For subjects consenting to the optional biomarker sample, blood will be collected for the evaluation of biomarkers (specific targets to be determined) at Baseline, Week 3 Visit, and at the Week 51 Visit for subjects participating in the Optional Extension Phase (or upon early termination if prior to Week 51). These samples will be shipped to the central laboratory for processing and storage prior to analysis.

For subjects consenting to whole genome sequence analysis, a blood sample will be collected at Baseline. These samples will be shipped to the central laboratory for processing and storage prior to analysis. Whole genome sequences will be analyzed for genetic markers that may be associated with clinical response and tolerability.

Samples for the optional biomarker and optional whole genome sequencing will be coded in a manner that allows them to be matched to a study site and/or a subject number, but will not carry personal identifiers that could be traced to a specific individual. Complete instructions regarding the processing, packaging, and shipping of samples will be provided in a separate laboratory manual.

3.3.2 Safety and Tolerability Assessments

Safety assessments include incidence and severity of reported AEs, as well as changes from screening in vital signs, clinical laboratory tests, ECGs, and PEs.

3.3.2.1 Inspiratory Criteria Assessment

The subject's ability to perform inhalation maneuvers will be assessed at the Screening Visit and the Baseline Visit. Subjects must be able to perform inhalation maneuvers using the BluHale® technology that meets inspiratory training criteria. Subjects who are not able to demonstrate proper technique will be considered screen failures.

3.3.2.2 Medical History and Physical Examinations

A complete medical history (including pulmonary hypertension history), demographics, and PE (including an oropharyngeal exam) will be conducted during the Screening Visit. Significant past or present illnesses, current prescription or nonprescription medications (including vitamins and herbal products), and history of allergies or idiosyncratic responses to drugs should be recorded. Any significant changes to the subject's medical condition and physical examination must be documented throughout the course of the study. A complete PE will be conducted by appropriate study personnel at the Screening Visit, Baseline Visit, Week 3 Visit, and the Early Termination Visit. For subjects continuing in the Optional Extension Phase, a physical exam will conducted at each Extension Visit. Any clinically significant changes from Baseline noted during the study should be reported as AEs.

3.3.2.3 Vital Signs

Vital signs will be assessed at study visits as specified in Table 3-1. Vital signs measured will include blood pressure (systolic and diastolic), HR, respiratory rate (RR), and weight. Vital signs must be assessed following at least 5 minutes of rest (sitting) to ensure accurate measurement. No other measurements or procedures should be performed during this 5-minute period. When possible, vital signs should be collected prior to the 6MWT. If vital signs cannot be obtained prior to the 6MWT, then they should be obtained after recovery from the 6MWT. Vital signs should also be assessed and reported in the case of abnormal clinical signs and symptoms.

3.3.2.4 12-Lead Electrocardiogram

A 12-lead ECG will be recorded after at least 5 minutes of rest at the Baseline Visit and End of Study Visit or Early Termination Visit. Recordings should include lead II as a rhythm strip and contain at least 5 QRS complexes. ECG parameters to be collected include rhythm, HR, PR interval, QT interval, QRS duration (uncorrected), and any clinically significant abnormalities.

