7.5 END OF STUDY VISIT AND/OR EARLY TERMINATION VISIT

If a subject elects to discontinue TreT at the end of the Treatment Phase, an End of Study Visit must be completed within 2 weeks (±3 days). If a subject is discontinued from the study prematurely, an Early Termination Visit should be completed as soon as possible. Subjects who permanently discontinue TreT are encouraged to undergo premature termination assessments prior to discontinuing TreT or as close as possible to the last dose of TreT. The following activities will be performed:

- Administration of PQ-ITD (TreT assessment; only for subjects that discontinue during the 3-week Treatment Phase)
- Administration of PAH-SYMPACT Questionnaire
- Physical examination
- Vital signs (following at least 5 minutes of rest), including weight, RR, HR, SBP, and DBP
- Urine pregnancy test for WOCBP
- Blood draws for clinical laboratory parameters
- 12-lead ECG (following at least 5 minutes of rest)
- Peak 6MWT (should be conducted between 10 to 60 minutes after the most recent dose and following at least 10 minutes of rest [sitting])

- Dosing diary/TreT accountability
- AE assessment
- Concomitant medications

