# 6 SEQUENCE OF PLANNED ANALYSES

After all subjects complete the Treatment Phase, the Treatment Phase database will be locked and analysis of the data from the Treatment Phase will be carried out. Any available data from the Optional Extension Phase will also be analyzed at this time. At the completion of the study, final analyses of the Optional Extension Phase data will be conducted.

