# 12.5 ELECTROCARDIOGRAMS

All ECG assessments will be listed for all subjects. This listing will include the HR, the ECG interval from the beginning of the QRS complex to the end of the T wave (QT interval), the QT interval corrected for HR (QTc) (calculated using formulas by both Bazett and Fridericia as described in Section 9.5.2), the time between the P wave and the beginning of the QRS complex in ECG (PR interval), the electrocardiographic wave (QRS) duration, ECG results (normal/abnormal), whether there were clinically significant changes from the Screening Visit, whether abnormalities were present, and details and comments on any abnormalities. The ECG results at Baseline and changes for each post-Baseline assessment will be descriptively summarized by TreT dose and overall at each visit during the Treatment Phase and Optional Extension Phase. In addition, for QTc intervals calculated using both the Bazett and Fridericia methods, the number and percent of subjects with values ≥500 msec and the number and percent of subjects with changes from Screening of <30 msec, 30 to <60 msec, and ≥60 msec will be presented. Additionally, each abnormality will be summarized by the number and percentage of subjects reporting at each visit by TreT dose and overall at each visit during the Treatment Phase and Optional Extension Phase.

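### No 12-lead ECG is scheduled at any routine visit on TreT, and the SAP does not separate on-TreT from off-TreT tracings

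*Protocol*

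**What the plan says.** The primary objective is the safety and tolerability of TreT, and SAP 2.2 lists the 12-lead ECG as an endpoint. Protocol 3.3.2.4 states that the ECG "will be recorded after at least 5 minutes of rest at the Baseline Visit and End of Study Visit or Early Termination Visit". The ECG row of Protocol Table 3-1 agrees, and the activity lists for Week 3 (7.4) and the extension visits (7.6.1) contain no ECG.

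A subject who does not enter the extension stops TreT, may go back to Tyvaso, and "must return to the clinic 2 weeks after TreT discontinuation for an End of Study Visit" (Protocol 3.1). For the extension, Protocol 3.1 says: "Subjects who discontinue TreT must complete an Early Termination Visit as soon as possible". Protocol 7.5 adds that subjects who stop TreT for good are "encouraged to undergo premature termination assessments prior to discontinuing TreT or as close as possible to the last dose of TreT".

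SAP 12.5 plans that ECG "changes for each post-Baseline assessment will be descriptively summarized by TreT dose and overall at each visit during the Treatment Phase and Optional Extension Phase". It also plans QTc change categories measured from Screening. For ECGs, SAP Table 9-2 has only two windows: Baseline, and an End of Study window that takes the last tracing after Study Day 1.

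**The concern.** Physical examination, vital signs and laboratory tests are all scheduled at Week 3 and at every extension visit. The ECG is not, although the extension encourages upward titration of TreT. The tracings that do exist after Baseline mix two states: subjects who have stopped TreT and may be back on Tyvaso, and subjects who are terminating early and may or may not still be on TreT.

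The SAP puts both kinds in one window and tabulates them by TreT dose in Tables 14.3.3.2 and 14.3.3.3. A clean table would naturally be read as showing that TreT leaves QTc, rhythm and conduction unchanged, when many of its tracings, possibly nearly all, were taken off TreT.

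**Working it through.** The plan gives no ECG-specific figure to reproduce, and its sample size of 45 is stated not to rest on a power calculation. The check is a cross-reading of the schedule, followed by simple counts.

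**Step 1. Where ECGs fall** (Protocol Table 3-1, 3.3.2.4, 7.1 to 7.6)

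| Visit | ECG scheduled | Treatment status |
|---|---|---|
| Separate Screening | No | On Tyvaso |
| Baseline, or combined Screening/Baseline | Yes | Listed before the in-clinic Tyvaso dose and the first TreT dose |
| Week 3 | No | On TreT |
| Week 11, then every 8 weeks | No | On TreT |
| End of Study | Yes | TreT stopped, Tyvaso possible |
| Early Termination | Yes | On or off TreT |

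Routine on-TreT visits with an ECG: 0.

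**Step 2. Time off TreT at the End of Study Visit.** Protocol 3.1 puts the visit 2 weeks after TreT is stopped. With the ±3-day window, that is 14 − 3 = 11 to 14 + 3 = 17 days. Protocol 7.5 and Table 3-1 footnote k instead require completion within 2 weeks (±3 days), which sets no lower limit. Both readings place the visit after TreT is stopped; only the first gives 11 days as a minimum.

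**Step 3. What is available at the first analysis.** SAP 6 says: "After all subjects complete the Treatment Phase, the Treatment Phase database will be locked". The documents do not give extension uptake, so take it as an assumed fraction u. Leave early terminations aside, and assume that decliners' End of Study ECGs are in the database. The number with any post-Baseline ECG is 45 × (1 − u), rounded down. For scale, the one-sided 95% upper limit on an event rate when no event is seen is 1 − 0.05^(1/n).

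| Assumed uptake | n with a post-Baseline ECG | Upper limit, 0 events |
|---|---|---|
| 50% | 22 | 12.7% |
| 80% | 9 | 28.3% |
| 90% | 4 | 52.7% |
| 100% | 0 | not estimable |

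All of these tracings are off TreT, so the limits do not describe TreT even where they exist.

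**Step 4. What a Week 3 ECG would give.** With all 45 subjects, the limit is 1 − 0.05^(1/45) = 6.4%. SAP 1.2 says 20 subjects were enrolled before the pandemic hold. SAP 1.2.1 says all of them except 3 who could not provide Week 3 PK assessments had completed the Week 3 Visit before the closures. An amendment taking effect when enrolment resumed could reach at most 45 − 20 = 25 subjects, for a limit of 1 − 0.05^(1/25) = 11.3%. A later amendment reaches fewer.

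**Step 5. The SAP against the schedule.** SAP 12.5 asks for summaries at each visit of both phases, but Table 9-2 has no ECG window for Week 3 or any extension visit. SAP 12.5 takes QTc change from Screening, but only the combined Screening/Baseline Visit has an ECG. SAP 9.5.1 already defines Baseline as the Baseline Visit measurement.

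**Step 6. The closing visit.** Protocol 7.5 names two triggers: stopping at the end of the Treatment Phase, and premature discontinuation. A subject still on TreT when the study ends or the product is marketed fits neither clearly. Protocol 3.3.2.6, however, describes the final study visit as End of Study or Early Termination, and 6.2 runs the dosing diary through the End of Study Visit.

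**The case against.** The strongest reply is that this is a Phase 1b switch in subjects already taking inhaled treprostinil, with no QT objective. The single-dose TreT study in Protocol 1.2.3.2 reported no clinically significant ECG abnormalities at 30 to 180 µg, and Treatment Phase doses are 32 to 64 µg. This lowers the urgency. It does not close the gap, because that study gave one dose to each of 36 healthy volunteers. It says nothing about repeated dosing in PAH.

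SAP 9.6 also makes Table 9-2 govern anything summarised by visit, so the wording in SAP 12.5 would not generate a spurious Week 3 ECG result. That stands: the two sections need aligning, but no false row would appear.

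A reader might infer four stronger claims that the documents do not support:

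- **That every post-Baseline ECG is off TreT or missing.** Early Termination tracings are encouraged before or near the last dose, so some may be on TreT. They are not guaranteed and come only from subjects who discontinue.
- **That subjects who stay to study end never have a second ECG.** Step 6 shows an ambiguity, not a demonstrated absence.
- **That no effect on heart rate can be seen.** Heart rate is a vital sign at Week 3 and at every extension visit, and SAP 12.4 summarises its change.
- **That End of Study tracings are fixed at 11 to 17 days off drug.** The wording in Protocol 7.5 does not set that minimum.

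**Conclusion.** The point holds in a limited form. No routine on-TreT visit has an ECG. As written, the ECG tables cannot describe QTc, intervals, rhythm or conduction on TreT, except through an unplanned and selected set of Early Termination tracings that the SAP does not separate out. The by-visit wording and the Screening reference in SAP 12.5 do not match the schedule, and the closing visit for subjects still on TreT at study end is unclear.

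The count of zero rests on the schedule alone. The numbers at the Treatment Phase lock (22, 9, 4 or 0) rest on assumed extension uptake and on leaving early terminations aside. This should be corrected before the ECG tables are produced. It does not touch the AE, laboratory or vital-sign results.

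**What to change.** 1. In SAP Table 9-2, SAP 12.5 and Tables 14.3.3.2 and 14.3.3.3, present post-Baseline ECGs separately as on TreT or off TreT, with days since the last dose. Do not present off-TreT tracings as TreT safety results. The last-dose date is already in the accountability listing (SAP 10.1), so this costs SAP wording and programming only, and it can be done without a protocol amendment.
2. In SAP 12.5, make Baseline the reference for QTc change, and limit the by-visit wording to visits that have an ECG. This is wording only.
3. For subjects not yet past Week 3, amend Protocol Table 3-1, 3.3.2.4 and 7.4 to record an ECG at that visit, with its time since the last TreT dose, and add a Week 3 ECG window to SAP Table 9-2. The Baseline ECG is listed before the in-clinic dose, and the predose PK sample should be at least 4 hours after the previous dose. A tracing matched to Baseline would therefore reflect trough exposure, and the report should say so. For decliners it can replace the End of Study ECG. Extension entrants have one short extra tracing at a visit where PK sampling already runs from −15 to 300 minutes. The downside is a partial sample if the amendment comes late (at most 25 of 45 by Step 4).
4. Reconcile Protocol 7.5 with 3.3.2.6 and 6.2 so that it is clear which closing visit, and hence whether an ECG, applies to subjects still on TreT when the study ends.
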